The protocol and informed consent forms will be submitted to the FMOS/FAPH Ethics Committee (EC) for review and approval. Approval of both the protocol and the consent forms must be obtained before any subject is enrolled. Any amendment to the protocol will require review and approval by the EC before the changes are implemented to the study. In addition, all changes to the consent forms will be EC-approved; a determination will be made regarding whether a new consent needs to be obtained from subjects who provided consent using a previously approved form.

Version Date: 14 March 2024

1 PROTOCOL SUMMARY

1.1 Synopsis

Title: Safety and Efficacy of L9LS, a Human Monoclonal Antibody

Against *Plasmodium falciparum*, in a Dose-Escalation Trial in Adults and Children and a Randomized, Double-Blind Trial of

Children in Mali

Study Description:

A two-part, phase 2 trial evaluating the safety and tolerability of one-time subcutaneous (SC) or intravenous (IV) administration of monoclonal antibody (MAb) L9LS in healthy Malian adults and one-time SC administration of L9LS in healthy Malian children, as well as its protective efficacy against naturally occurring *Plasmodium falciparum* (Pf) infection over a 7-month malaria season in healthy Malian children 6-10 years of age. The primary study hypotheses are that L9LS will be safe and will produce protection against malaria infection when administered prior to the malaria season. Before study agent administration, all subjects will be given artemether-lumefantrine to clear any preexisting Pf blood-stage infection.

Age de-escalation and dose-escalation study: The first part of the study is an age de-escalation and dose-escalation study for safety and tolerability. Adult subjects (N=18) in the dose-escalation study will be assigned in open-label fashion to 1 of 3 L9LS dose arms (n=6 for each dose level). Dosing will begin in the lowest dose arm (300 mg SC). Once all subjects in that arm reach day 7 post-administration, if no safety concerns have arisen, dosing will begin at the next dose level (600 mg SC). Once all subjects in that arm reach day 7 post-administration, if no safety concerns have arisen, dosing will begin at the highest dose level (20 mg/kg IV). Once all adult subjects reach day 7 post-administration, if no safety concerns have arisen, 18 subjects aged 6-10 years will be randomized 1:1 in double-blind fashion to 150 mg of L9LS SC (n=9) versus placebo SC (n=9). Once all 18 subjects reach day 7 post-administration, if no safety concerns have arisen, an additional 18 subjects aged 6-10 years will be randomized 1:1 to 300 mg of L9LS SC (n=9) versus placebo SC (n=9). Randomization of subjects aged 6-10 years in each L9LS dose arm will be weight-stratified (26-30 kg, n=6; 20-25 kg, n=6; 15-19 kg, n=6) and enrollment will be weight de-escalated starting with

subjects weighing 26-30 kg. Adult subjects will be followed for safety to assess adverse events (AEs) at study visits 1, 3, 7, 14, 21, and 28 days after administration, and once every month thereafter through 28 weeks. Subjects aged 6-10 years will be followed at study visits 1, 3, 7, 14, 21, and 28 days after administration, and once every 2 weeks thereafter through 28 weeks. Primary study assessments include physical examination and blood collection for identification of Pf infection and other research laboratory evaluations. After the last subject in the pediatric 300-mg L9LS dose arm reaches day 7 safety follow-up, an interim safety evaluation will be performed before enrollment begins for the efficacy part of the study. Data from the 36 subjects aged 6-10 years enrolled in the dose-escalation study will be included in a secondary analysis to determine the relationship between L9LS concentration and the risk of Pf infection. For these 36 subjects, blinding will be maintained for treatment assignment (L9LS versus placebo), but not for possible L9LS dose group.

Efficacy study: The second part of the study is a weight-stratified, randomized, double-blind, placebo-controlled trial (N=225 total, n=75 for each of 2 treatment arms, n=75 for placebo arm) to assess safety and protective efficacy of L9LS and placebo administered SC in children 6-10 years of age. In this part of the study, 225 subjects will be randomized 1:1:1 to 150 mg of L9LS (n=75), 300 mg of L9LS (n=75), or placebo (n=75). Randomization of subjects in each arm will be weight-stratified (26-30 kg, n=75; 20-25 kg, n=75; 15-19 kg, n=75). Subjects in the efficacy study will receive the study agent prior to the malaria season and be followed at study visits 1, 3, 7, 14, 21, and 28 days later, and once every 2 weeks thereafter through 24 weeks. Primary study assessments include physical examination and blood collection for identification of Pf infection and other research laboratory evaluations.

Year 2 extension: Prior to the last study visit of the original protocol described above (January 2023 - February 2023), study participants who remain enrolled in the dose-escalation and efficacy studies will be invited to participate in a 12-month extension study. After the safety and efficacy results are unblinded (approximately March/April 2023), participants who agree to continue with the extension will be grouped into one of 3 arms based on their original study arm assignment:

Arm 1: Up to 84 subjects who received 150 mg of L9LS in year 1 (9 from the dose-escalation study, plus 75 from the efficacy study).

Arm 2: Up to 84 subjects who received 300 mg of L9LS in year 1 (9 from the dose-escalation study, plus 75 from the efficacy study).

Arm 3: Up to 93 subjects who received placebo in year 1 (18 from the dose-escalation study, plus 75 from the efficacy study).

The protocol extension employs a pre-specified, adaptive design based on the time-to-event efficacy of 150 mg and 300 mg of L9LS against *P. falciparum* infection as detected by blood smear observed after the first malaria season in the original protocol. Specifically, if 150 mg and 300 mg of L9LS both show ≥60% efficacy during the first malaria season (based on the upper bound of the two-sided 95% confidence interval [CI]), participants will be re-randomized 1:1 in a double-blind fashion within each arm to receive a single dose of either L9LS (150 or 300 mg depending on study arm) or placebo administered SC before the 2023 malaria season.

The same randomization scheme will be followed if in the first malaria season the 300-mg dose of L9LS shows \geq 60% efficacy (based on the upper bound of the two-sided 95% CI) and the 150-mg dose of L9LS shows <60% efficacy (based on the upper bound of the two-sided 95% CI) but the difference between their respective point estimates of efficacy is \leq 10%, with the exception that children who received placebo in year 1 will receive 300 mg of L9LS (or placebo) in year 2.

If 300 mg of L9LS shows ≥60% efficacy (based on the upper bound of the two-sided 95% CI) and 150 mg of L9LS shows <60% efficacy (based on the upper bound of the two-sided 95% CI) but the difference between their respective point estimates of efficacy is >10% during the first malaria season, participants will be rerandomized 1:1 in a double-blind fashion within each arm to receive a single dose of either 300 mg of L9LS or placebo administered SC before the 2023 malaria season.

If 150 mg and 300 mg of L9LS both show <60% efficacy (based on the upper bound of the two-sided 95% CI) after the first malaria season, the protocol extension will be abandoned.

Before study agent administration, all subjects will be given artemether-lumefantrine to clear any preexisting Pf blood-stage infection.

Subjects will be followed at study visits 1, 3, 7, 14, 21, and 28 days after administration, and once every 2 weeks thereafter through 28 weeks, with a final visit occurring on study day 252 (36 weeks) to collect a final PK sample. Primary study assessments include medical history, physical examination, and blood collection for pharmacokinetics (PK), anti-drug antibody (ADA) assessments, identification of Pf infection by microscopic examination of thick blood smears and RT-PCR, and other research laboratory evaluations.

Objectives:

Primary Objectives:

- Dose escalation: To evaluate the safety and tolerability of L9LS administered at 300 mg and 600 mg SC and 20 mg/kg IV in healthy Malian adults, and at 150 mg and 300 mg SC in healthy Malian children.
- 2. Efficacy: To evaluate the safety and tolerability of L9LS administered at 150 mg and 300 mg SC in healthy Malian children.
- 3. Efficacy: To determine if SC administration of L9LS at 150 mg and 300 mg (compared to placebo) mediates protection against naturally occurring Pf infection in healthy Malian children during a single malaria season as detected from microscopic examination of thick blood smear.

Secondary Objectives:

Data from both parts of this study will be used to address the following objectives:

 To evaluate the PK of L9LS throughout the study at dose levels of 300 mg and 600 mg SC and 20 mg/kg IV in healthy Malian adults, and at 150 mg and 300 mg SC in healthy Malian children, and to correlate L9LS serum concentration with Pf infection risk.

2. To determine if SC administration of L9LS at 150 mg and 300 mg (compared to placebo) mediates protection against naturally occurring Pf infection in healthy Malian children during a single malaria season as detected by reverse transcription polymerase chain reaction (RT-PCR).

- 300 mg (compared to placebo) mediates protection against clinical malaria in healthy Malian children during a single malaria season as defined by an illness accompanied by measured axillary fever ≥37.5°C, or history of fever (subjective or objective) in the previous 24 hours, and Pf asexual parasitemia >5,000 parasites/µL as detected from microscopic examination of thick blood smear.
- 4. To determine if SC administration of L9LS at 150 mg and 300 mg (compared to placebo) mediates protection against clinical malaria in healthy Malian children during a single malaria season as defined by an illness accompanied by any level of Pf asexual parasitemia as detected from microscopic examination of thick blood smear that results in the administration of anti-malarial treatment.
- 5. To evaluate the PK of L9LS throughout the study at the dose of 150 mg and 300 mg and to correlate L9LS serum concentration with Pf infection risk.
- 6. To evaluate the PK of L9LS throughout the study at the dose of 150 mg and 300 mg and to correlate L9LS serum concentration with clinical malaria risk.

Extension Phase Primary Objectives:

- 1. To evaluate the safety and tolerability of a second SC dose of L9LS administered at 150 mg and 300 mg (compared to placebo) in healthy Malian children.
- 2. To evaluate the PK of L9LS throughout the study at dose levels of 150 mg and 300 mg SC in healthy Malian children.
- 3. To determine if ADAs to L9LS can be detected in sera of recipients at specific timepoints throughout the study and to correlate the occurrence of ADAs with L9LS PK.

Extension Phase Exploratory Objectives (see Figure 3 for study arm definitions):

- 1. To assess the efficacy of a second SC dose of L9LS at 150 mg and 300 mg (compared to placebo) in mediating protection against Pf infection and clinical malaria in healthy Malian children during a second malaria season (arms 1a vs. 1b; arms 2a vs. 2b), and to assess if this efficacy is influenced by whether or not a prior dose of L9LS was administered in year 1 (arms 1a vs. 3b; arms 2a vs. 3b).
- 2. To assess the efficacy of a first SC dose of L9LS at 150 mg or 300 mg (compared to placebo) in mediating protection against Pf infection and clinical malaria in healthy Malian children during the second malaria season (arms 3a vs. 3b).
- 3. To assess the risk of clinical malaria in children who received L9LS in year 1 but not year 2 (compared to children who received placebo both years; arms 1b vs. 3b; arms 2b vs. 3b).
- 4. To evaluate the PK of L9LS throughout the study at the dose of 150 mg and 300 mg and to correlate L9LS serum concentration with Pf infection risk.
- 5. To evaluate the PK of L9LS throughout the study at the dose of 150 mg and 300 mg and to correlate L9LS serum concentration with clinical malaria risk.

Endpoints:

Primary Endpoints:

- 1. Dose escalation and efficacy: Incidence and severity of local and systemic AEs occurring within 7 days after the administration of L9LS.
- 2. Efficacy: Pf blood-stage infection as detected by microscopic examination of thick blood smears obtained between 1 week and 24 weeks after administration of L9LS or placebo.

Secondary Endpoints:

Data from both parts of this study will be used to assess the following endpoints:

- 1. Measurement of L9LS in sera of recipients.
- 2. Pf blood-stage infection as detected by RT-PCR for 28 weeks after administration of L9LS or placebo for dose escalation subjects or 24 weeks after administration of L9LS or placebo for efficacy subjects.

- 3. Incidence of clinical malaria (definition 1, see section 2.2.2.3) for 28 weeks after administration of L9LS or placebo for dose escalation subjects or 24 weeks after administration of L9LS or placebo for efficacy subjects.
- 4. Incidence of clinical malaria (definition 2, see section 2.2.2.3) for 28 weeks after administration of L9LS or placebo for dose escalation subjects or 24 weeks after administration of L9LS or placebo for efficacy subjects.
- 5. PK analysis of L9LS and the association of L9LS concentration with Pf infection risk.
- 6. PK analysis of L9LS and the association of L9LS concentration with clinical malaria risk.

Extension Phase Primary Endpoints:

- 1. Incidence and severity of local and systemic AEs occurring within 7 days after the administration of L9LS.
- 2. Measurement of L9LS in sera of recipients.
- 3. Measurement of ADA in sera of recipients.

Extension Phase Exploratory Endpoints:

- 1. Pf blood-stage infection as detected by microscopic examination of thick blood smears obtained between 1 week and 28 weeks after administration of L9LS or placebo.
- 2. Pf blood-stage infection as detected by RT-PCR from dried blood spots obtained between 1 week and 28 weeks after administration of L9LS or placebo.
- 3. Incidence of clinical malaria (definition 1, see section 2.2.2.3) between 1 week and 28 weeks after administration of L9LS or placebo.
- 4. PK analysis of L9LS and the association of L9LS concentration with Pf infection risk.
- 5. PK analysis of L9LS and the association of L9LS concentration with clinical malaria risk.

Study Population:

Healthy Malian adults (aged ≥18 to 55 years) and children (aged 6 to 10 years) residing in Kalifabougou and Torodo who are not receiving seasonal malaria chemoprevention (SMC).

The year 2 extension phase will include only participants who are currently enrolled in the study and agree to continue in the extension.

Version Date: 14 March 2024

Phase: 2

Description of Sites/Facilities Enrolling Participants:

The MRTC clinics in Kalifabougou and Torodo. All screening, day 0 (study agent administration), and day 14 visits will be performed at Kalifabougou only. Both sites will conduct recruitment, enrollment, follow-up visits (other than day 14 as noted above), and unscheduled

study visits.

For the year 2 extension phase, all day 0 (study agent administration) will be performed at Kalifabougou only. Both sites (Kalifabougou and Torodo) will conduct recruitment, enrollment, follow-up visits, and unscheduled study visits.

Description of Study Intervention:

The study agent will be administered as a one-time SC injection or IV infusion as follows: L9LS at a dose of 150 mg SC (children only), 300 mg SC (children and adults), 600 mg SC (adults only), or 20 mg/kg IV (adults only), or matching placebo (children only).

In the year 2 extension phase, the study agent will be administered as a one-time SC injection as follows: L9LS at a dose of 150 mg or 300 mg, or matching placebo.

Study Duration:

36 months.

Participant Duration:

7 months for dose escalation subjects (plus 2 months for those in the pediatric dose-escalation cohort who agree to additional follow-up visits, see Appendix E); 6 months for efficacy subjects.

Year 2 extension phase: 12 months from the time of enrollment in the extension.

Version Date: 14 March 2024

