9.5.1.1 Year 2 Extension Study

The same analysis methods for safety, PK, and efficacy endpoints described for the original study (year 1) below will be applied to the year 2 extension study. There will be no multiplicity adjustment in extension study analyses. All comparisons will be conducted at two-sided significance level 0.05.

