APPENDIX E: DOSE ESCALATION PEDIATRIC STUDY EXTENSION

Study Extension Rationale

Pediatric participants who are enrolled in the Dose Escalation study may be followed with additional study visits through the end of the malaria season to 1) determine whether they become infected with *P. falciparum* (as detected by RT-PCR from dried blood spots collected every 4 weeks), and 2) extend the PK analysis of L9LS to approximately 9 months (as determined by measuring the concentration of L9LS in blood samples collected every 4 weeks). The Pediatric Dose Escalation component of the study had 2 dose groups (150 mg of L9LS or placebo and 300 mg of L9LS or placebo). Following all subjects in the Pediatric Dose Escalation group will allow for exploratory analyses that assess the correlation between L9LS serum concentrations and *P. falciparum* infection risk over a 9-month period. Since these participants received study agent earlier than participants in the efficacy study, they are expected to have lower serum L9LS concentrations at the end of the malaria season compared to participants in the efficacy study, which will allow for correlations of malaria risk over a broader range of L9LS concentrations.

Study Extension Procedures

Pediatric participants who are enrolled in the Dose Escalation study will be offered participation in the extension study visits and undergo an informed consent process (see section 10.1.1.2) with the ICF addendum. Those that agree to participate will be enrolled and begin monthly Extension study visits at the MRTC clinic in Kalifabougou or Torodo. At each study visit, up to 1.0 mL of blood will be collected by venipuncture for blood smear, Pf RT-PCR, possible parasite genotyping in the case of a positive malaria parasite infection (see section 8.2.3), and measurement of L9LS concentrations in serum. If a participant develops symptoms of malaria or other symptoms, they will be asked to return for an illness visit (see section 8.2.1). AEs related to the blood collection procedures and all SAEs will be collected and followed through resolution.

Participants will attend monthly study visits through Day 252, for a total of 2 monthly extension visits.

Compensation

Subjects will be compensated 3,000 Communauté Financière Africaine (CFA) Franc for each study visit for the time and inconvenience of participation. Payment will be provided in cash after the completion of each visit.

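### Year-2 contrasts between arm 3 and arms 1 or 2 pool three Year-1 randomizations in unequal shares with no stated stratum, so the Year-1 randomization does not fully protect them; the likely bias is small.

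*Combined protocol and SAP*

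**What the plan says.** Children were randomized in Year 1 on three occasions (section 1.1):

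- dose escalation, first cohort: "18 subjects aged 6-10 years will be randomized 1:1 in double-blind fashion to 150 mg of L9LS SC (n=9) versus placebo SC (n=9";
- dose escalation, second cohort, begun once the first had passed day 7: "an additional 18 subjects aged 6-10 years will be randomized 1:1 to 300 mg of L9LS SC (n=9) versus placebo SC (n=9";
- efficacy part: "225 subjects will be randomized 1:1:1 to 150 mg of L9LS (n=75), 300 mg of L9LS (n=75), or placebo (n=75".

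The extension groups children by Year-1 treatment, whichever randomization they came from:

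- those treated with the lower dose form arm 1, described as "Up to 84 subjects who received 150 mg of L9LS in year 1 (9 from the dose-escalation study, plus 75 from the efficacy study";
- those treated with the higher dose form arm 2, described as "Up to 84 subjects who received 300 mg of L9LS in year 1 (9 from the dose-escalation study, plus 75 from the efficacy study";
- those given saline form arm 3, described as "Up to 93 subjects who received placebo in year 1 (18 from the dose-escalation study, plus 75 from the efficacy study".

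The second randomization is 1:1 inside each of these arms. No stratification factor is stated for it; section 9.5.1 describes weight strata for the two Year-1 parts only.

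Sections 1.1 and 4.1.1 list five contrasts that cross arms: 1a vs 3a for safety, 1a vs 3b and 2a vs 3b for efficacy, 1b vs 3b and 2b vs 3b for rebound malaria. On method, section 9.5.1.1 says: "The same analysis methods for safety, PK, and efficacy endpoints described for the original study (year 1) below will be applied". Those methods (section 9.5.4) are a log-rank test, a Cox model, an additional Cox model with time of enrollment and possibly other imbalanced covariates, and a Cox model stratified by baseline parasitemia. Year-1 randomization is not named as a stratum or covariate anywhere.

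**The concern.** The Year-2 re-randomization makes 1a/1b, 2a/2b and 3a/3b comparable. It does nothing for a comparison of arm 1 or 2 with arm 3, which depends on how children came to their Year-1 arm. Inside each Year-1 randomization that was by chance. Once the three are pooled, the chance of having been on placebo depends on which study part a child joined.

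The parts are not identical. Dose-escalation children were recruited and dosed earlier and followed longer in Year 1. Appendix E notes one consequence: "Since these participants received study agent earlier than participants in the efficacy study, they are expected to have lower serum L9LS concentrations". Any difference in Year-2 risk between the parts would leak into the cross-arm contrasts and be read as an effect of Year-1 treatment. This matters most for rebound, where the expected effect may itself be modest, and for 1a vs 3a, which serves the primary safety objective of the extension.

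**Working it through.** **Inputs from the documents.** Arms 1 and 2: 9 + 75 = 84 each. Arm 3: 18 + 75 = 93 (section 1.1; all are maxima). Planned size per sub-arm for power: 42 (section 9.3). Table 7 infection rates: 0.5 to 0.7 in the higher-risk arm.

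**Step 1: reproduce Table 7.** Freedman's log-rank formula with hazard ratio ln(1−p2)/ln(1−p1), events 42 × (p1 + p2), two-sided 0.05 and no dropout. For 0.5 vs 0.2: HR = 0.322, events = 29.4, and √29.4 × (1 − 0.322)/(1 + 0.322) − 1.96 = 0.82, so power is 79.4% (stated 79). The six rows give 79.4, 90.0, 89.3, 95.8, 95.6 and 98.6%, against 79, 90, 89, 96, 96 and 99 stated. The figure 42 is 84/2, so Table 7 counts dose-escalation children.

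**Step 2: shares.** 9/84 = 10.7% and 18/93 = 19.4%, a gap of 8.6 points. In an arm 1 vs arm 3 comparison, the share on Year-1 placebo is 18/27 = 67% among dose-escalation children and 75/150 = 50% among efficacy children. If retention varies independently between 80% and 100% in the two study parts (assumed, equal across arms within a part), the shares run 8.8 to 13.0% in arms 1 and 2 and 16.1 to 23.1% in arm 3.

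**Step 3: size of the bias with no true effect.** Shift = (18/93 − 9/84) × (risk in dose-escalation children − risk in efficacy children). The documents give no Year-2 risk by study part, so the differences below are assumptions, applied in either direction to an efficacy-children risk of 0.5, 0.6 or 0.7 and kept below 100%.

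| Assumed difference | Shift in risk difference | Spurious HR | Type I error (nominal 0.05) |
|---|---|---|---|
| 10 points | 0.9 points | 0.976 to 1.026 | 0.051 |
| 20 points | 1.7 points | 0.952 to 1.053 | 0.053 to 0.054 |
| 30 points | 2.6 points | 0.930 to 1.082 | 0.057 to 0.058 |

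Example: risks of 0.5 (efficacy) and 0.2 (dose escalation) give 0.5 − 0.107 × 0.3 = 0.468 in arm 1 and 0.5 − 0.194 × 0.3 = 0.442 in arm 3. Then HR = ln(0.532)/ln(0.558) = 1.08. With 42 vs 46 children there are about 40 events, the test statistic moves by about 0.25, and the two-sided error is about 0.057.

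**Step 4: would the carried-over covariate rule catch it?** Section 9.5.4 adds covariates that differ significantly between arms. For 18/93 vs 9/84, the pooled proportion is 27/177 and z = 0.0864/0.0541 = 1.60, p = 0.11. With sub-arms half that size, z = 1.13, p = 0.26. The rule would not be expected to select study part.

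**Step 5: after stratification.** In arm 1 vs arm 3, the dose-escalation 300 mg stratum contains only placebo children, so it contributes nothing; the same holds for the 150 mg stratum in arm 2 vs arm 3. What remains is 9 + 75 against 9 + 75, a 10.7% share on both sides and about 42 vs 42 after the 1:1 split. That is the Table 7 size, so power is essentially unchanged. Using efficacy children only (about 37.5 per sub-arm) would give 74.8, 86.5, 85.7, 93.6, 93.4 and 97.6%, a loss of about 1 to 5 points.

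**The case against.** The best defence is that nothing in the documents shows that the two study parts differ in Year-2 risk. They share sites, eligibility criteria and equal weight bands, and in Year 2 all children follow one schedule with the same parasite clearance beforehand. The Appendix E remark concerns antibody levels late in Year 1, whereas the excess children in arm 3 received saline. All of this stands, and it is why the effect is judged small.

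Two pieces of carried-over text might seem to settle the matter. First, the additional Cox model includes time of enrollment. That would separate the study parts if it means Year-1 enrollment, but this is not stated, and it would not reach the log-rank test or the adverse-event proportions. Second, section 9.5.4 confines efficacy analyses to children of the efficacy study. Read literally, that removes the pooling for efficacy, but it conflicts with the arm definitions, Table 1 and the 42 per arm in section 9.3, and it does not govern safety.

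A reader might also infer more than the documents support:

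- *That the Year-1 randomization gives no protection.* It does: 75 of 84 and 75 of 93 children come from one 1:1:1 randomization, and assignment was random within each of the other two.
- *That the bias could be large.* If dose-escalation children had two or three times the risk, the arm 3 to arm 1 risk ratio would be off by 1.08 or 1.14. At the Table 7 infection rates of 0.5 to 0.7, doubling already reaches or exceeds 100% and tripling is impossible. For rarer outcomes such ratios are arithmetically possible, but the documents give no basis for them.
- *That the re-randomization is known to be unstratified, and that stratifying it would help.* The documents are silent on the first. On the second, the shares in each arm are fixed before re-randomization, so stratifying it cannot correct the imbalance between arms.

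**Conclusion.** The point holds in a limited form. The five cross-arm contrasts are not fully protected by the Year-1 randomization, because the share of dose-escalation children differs by design (19.4% vs 10.7% at full retention) and no planned analysis is stated to respect the three randomizations. Under assumed risk differences of 10 to 30 points between study parts, the shift is 0.9 to 2.6 points and the type I error at most about 0.058.

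Four of the five contrasts are exploratory; only 1a vs 3a bears on a primary objective, and its endpoint is adverse events within 7 days of dosing. The contrasts 1a/1b, 2a/2b, 3a/3b and the aggregate L9LS vs placebo safety comparison are unaffected. This is a worthwhile refinement, not a threat to the extension's conclusions.

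One limit remains whatever is done: joining Year 2 is a choice made after Year-1 treatment, so uneven retention could still weaken these contrasts.

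**What to change.** In section 9.5.1.1:

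1. State that every comparison of arm 1 or 2 with arm 3 (log-rank, Cox and adverse-event proportions) is stratified by Year-1 randomization, with three levels: dose-escalation 150 mg, dose-escalation 300 mg, efficacy. Two levels (dose escalation vs efficacy) would not do, since they set 9 treated children against 18 placebo children, half of whom were randomized against the other dose.
2. State whether the section 9.5.4 restriction of efficacy analyses to efficacy-study children applies in Year 2, and reconcile it with the arm definitions and section 9.3.

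This version is dated 14 March 2024 and re-dosing was planned before the 2023 season. If Year-2 data are already unblinded, report the stratified results as a labelled sensitivity analysis.

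The cost is a few sentences and no new data. In each contrast, 9 dose-escalation placebo children (about 4 to 5 per sub-arm) drop out of the information, and the remaining dose-escalation stratum is thin, at about 4 to 5 per sub-arm. The comparison stays at about 42 vs 42, so the stated power is essentially unchanged.
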